#### **Secondary Objectives**

The sample size for Secondary Objective 1 will be guided by that of the Primary Objectives as detailed above.

The sample size for Secondary Objective 2 will be limited to a maximum of 27 neonatal units within the London Neonatal Operational Delivery Network, as listed above.

Secondary Objective 3 will include 2 qualitative data groups. The parent survey, focus groups and semi-structured interview sample sizes will be limited to the number of parent / carer participants eligible for inclusion into the quantitative data section as detailed above. Therefore an approximate minimum of 560 parents will be given the option to register interest for inclusion. A small representative sample of these will be included in focus groups and semi-structured, in depth-interviews.

## 10.2. Method of analysis

Due to the *a priori* nature of the sample size calculations, these will be redone based on interim data. This is suggested once each hospital has at least 10 participants. Then a readjustment shall be done every two-three months until sample size has been reached for both primary objectives. This will include the use of bilirubin measures, skin tone and age at TcB measurement, but no other data. The statistician will provide the study leads with the updated targets with no other interim analysis. This may reduce or extend study length depending on the targets of both primary objectives.

Data will be analysed on exposure in accordance with the allocation on skin colour scale. We expect limited missing data. If missing data is <5% for any covariate then analysis will be restricted to complete case analysis. Multiple imputation will only be used if missing data is >5% for any category.

All data collated will be presented in summary tables, stratified by skin colour. Continuous data will be summarised in terms of the mean, standard deviation (SD), median, minimum, maximum and number of observations, when the data are approximately normally distributed.. Continuous data that are expected to be skewed will be presented in terms of the maximum, upper quartile, median, lower quartile, minimum and number of observations. The minimum and maximum will be reported to the same number of decimal places as the raw data recorded in the database. The mean, median, lower quartile and upper quartile will be reported to one more decimal place than the raw data recorded in the database. The SD will be reported to two more decimal places than the raw data recorded in the database. In general, the maximum number of decimal places reported shall be four for any summary statistic. Categorical data will be summarised in terms of the number of participants providing data at the relevant time point (n), frequency counts and percentages. The number of participants with missing information for a specific variable will be displayed if applicable. Any planned collapsing of categories will be detailed in the SAP text and the data displays. Percentages will be presented to one decimal place. Percentages will not be presented for zero counts. Percentages will be calculated using non-missing data as the denominator. Confidence intervals (CI) will be presented to one more decimal place than the raw data.

Primary objective 1 will be using a linear mixed model, with skin tone and confounders as fixed effects and hospital as a random effect. The outcomes will be the coefficient difference between baseline skin tone and the other 3, with 95% CI.

Primary objective 2 will use the Bland-Altman to detect differences of measurement between skin tones, stratified by method of how the measurement for how serum bilirubin was taken. The mean of the differences will be provided with 95% CI, along with the IQR of difference with accompanying p-value. The rate of over/under-estimation will also be estimated between different skin tones. Bland-Altman plots will be reported as well as Specificity and sensitivity analyses using Receiver operating characteristic (ROC) curves.

Secondary Objective 1: Primary length of admission differences between skin tone will be compared using survival analysis of time to event data (Kaplan-Meier plot, Cox Proportional Hazards Model). The need for interventions including phototherapy and exchange transfusion will be done using generalised linear mixed models, with outcomes reported as Odds Ratios with 95% CI.

Age of infant at measurement is an important metric and shall be included as a fixed covariate in all models other than Bland-Altman (baseline model). Additionally, IMD and gestational age may be included as additional covariates (adjusted model). However, due to the complex relationship between skin colour and medical intervention, we run the risk of over-adjusting on covariates and inducing collider bias and/or mediators. For example, skin tone may affect what the indication for jaundice assessment was, and this in turn may affect the outcome of bilirubin and if there was a delay for treatment, making it a mediator. With sufficient time, this relationship may be explored to see if different skin tones are affected by how their jaundice is first indicated, which influences clinical guidelines if an association is found between skin tone and indication which in turn affects bilirubin levels.

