Following initial sample size calculations (detailed in Section 10) it has been estimated that a total of 560 participants will need to be recruited, to adequately power the study's Primary Objectives 1 and 2. Therefore, we will aim to recruit a

minimum of 28 participants at each site. An initial recruitment window will aim to recruit 10 participants per site. If there is insufficient recruitment to particular skin tone groups, recruitment windows can be reopened in centres where recruitment of participants of that group is most likely.

Data collection periods may need to be staggered according to the timings of individual Trust R&D approval processes. The total anticipated time for the study is currently 18 months, of which approximately the first 9 months will include local site approval processes and data collection, followed by a 9 month period of analysis and preparation for dissemination (see Gantt chart attached for further detail).

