<sup>b 1, 2, 3 or 4 as per Maya-Enero et al.

<sup>c Visibly jaundiced (parent/carer noted), visibly jaundiced (HCP noted), risk factors, routine, unwell, incidental

<sup>dRole of staff member performing measurement, Value and units, Location on body, Brand and model of machine, Time of measurement, Date of measurement eRole of staff member performing measurement, Value and units, Value relative to treatment line (micromol/L above/below line), Type of SBR (blood gas, lab, spun bili),

Time of measurement, Date of measurement

fNo intervention, feeding plan implemented (e.g. not specified, breastfeeding support, top ups), repeat bilirubin assessment indicated at a later time point (with time point specified), commence single phototherapy, commence double phototherapy, admit to NICU

Received IVIG, received exchange transfusion

hWhich of the following investigations were performed and what were their results: DAT, G6PD, blood cultures, participant blood group, birthing parent's blood group.

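### The skin-tone comparison of TcB-SBR agreement takes no account of TcB device model, body location or hospital, so any device or site differences could appear as, or mask, a tone effect

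*Protocol*

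**What the plan says.** Protocol section 10.2 sets the Objective 2 analysis: "Primary objective 2 will use the Bland-Altman to detect differences of measurement between skin tones, stratified by method of how the measurement" of serum bilirubin was made. Age at measurement "shall be included as a fixed covariate in all models other than Bland-Altman (baseline model"), so it is kept out of the agreement analysis. The only other covariates named are optional: "Additionally, IMD and gestational age may be included as additional covariates (adjusted model"). Hospital appears for the other primary objective: "Primary objective 1 will be using a linear mixed model, with skin tone and confounders as fixed effects and hospital as a random effect". No hospital term is named for Objective 2.

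The TcB details are collected. Table 1 in section 8 covers Primary Objectives 1 and 2, and its footnote on the TcB measurement lists "Location on body, Brand and model of machine". Section 10.2 also says that all collated data will be tabulated by skin colour, so these fields would at least be described.

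Section 10.1 assumes 20 hospitals. Section 8 adds that, if a tone group is under-recruited, "recruitment windows can be reopened in centres where recruitment of participants of that group is most likely".

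**The concern.** Objective 2 puts TcB under test, with SBR as the reference. The plan allows for variation in how the reference is measured but not in how the test is measured. TcB values come from routine care, and the protocol specifies neither a device nor a body site.

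A device or site difference biases the tone comparison only if it is associated with tone. Two features of the plan make that possible. Tone mix may vary between London hospitals, and reopened windows may draw scarce tones from particular centres. Where both conditions hold, a pooled tone-specific mean difference mixes device with tone. The study could then report that TcB over- or under-reads in darker skin because of the machines at certain hospitals, or could miss a real tone effect. More recruitment does not remove such a bias.

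**Working it through.** **The plan's own figures.** The protocol gives no figure for device bias, so there is none to reproduce on this point. Two planning values from section 10.1 serve as context: a mean difference of 10 and an SD of difference of √(43² + 38²) = 57.4. As a side check, the planned 140 participants do not reproduce. The usual limits-of-agreement calculation (limit 145, 95% CI of the limits, 80% power) gives 152, and power at 140 is 76.6%. The present point does not depend on this.

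**Where each variable is used (section 10.2).**

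| Variable | Collected | Tabulated by tone | In Objective 2 comparison |
|---|---|---|---|
| SBR method | yes | yes | stratifier |
| TcB device model | yes | yes | no |
| TcB body location | yes | yes | no |
| Hospital | yes | not stated | no (Objective 1 only) |

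Stratifying by SBR method would remove device differences only if SBR method happened to follow device.

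**Size of the artefact.** With two device types, spurious tone difference = (bias gap between devices) × (difference between tones in the share measured on one device). All gaps and shares below are assumptions.

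| Assumed gap (µmol/L) | Share difference 20 points | Share difference 40 points |
|---|---|---|
| 10 | 2 | 4 |
| 20 | 4 | 8 |
| 30 | 6 | 12 |

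Of these, only the 30 µmol/L gap at 40 points exceeds 10; at that gap the crossing point is 10/30, about 33 points.

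**Effect on error rate.** A simulation (2,000 runs per setting) assumed no true tone effect and two device types, each used in half the babies. Overall tone mix was the protocol's 50/20/20/10%, and tone 4 was compared with tone 1.

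- Moderate imbalance: tone 1 is 60% vs 40% and tone 4 is 6% vs 14% at the two site types. Shares on the second device are 0.40/1.00 = 0.40 and 0.14/0.20 = 0.70, a difference of 0.30. The artefact is 3 µmol/L for a gap of 10 and 6 for a gap of 20.
- Strong imbalance: tone 1 is 70% vs 30% and tone 4 is 3% vs 17%. Shares are 0.30 and 0.17/0.20 = 0.85, a difference of 0.55. The artefact is 5.5 or 11 µmol/L.

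False-positive rates with 560 paired babies, for gaps of 10 and 20:

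| SD of difference | Moderate | Strong | Same tone mix |
|---|---|---|---|
| 57.4 (protocol) | 6% and 10% | 9% and 24% | 4-6% |
| 25 (assumed) | 13% and 32% | 32% and 81% | 5-6% |

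With device type in the model, every setting returned to about 4-6%. The simulation included no hospital-to-hospital variation beyond device, and it gave every baby a pair.

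**The case against.** Several objections have force.

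- **Devices may not differ.** No section says that hospitals use different devices or body sites, or that these differ in bias against SBR. Recording brand, model and location makes variation plausible but does not establish it. This stands, and the point is conditional on it.
- **The data are not ignored.** A reader might infer that the device fields go unused. They do not: the summary tables by skin colour would show an imbalance. A table does not remove its effect on the comparison.
- **Reopening may not concentrate tones.** It is conditional, and section 8 says all eligible neonates are considered during data collection, so a reopened centre also adds other tones on the same devices. It may create an association between tone and device; it need not.
- **The magnitude is assumed.** This is so for every gap and share used. The 10 in section 10.1 is also a doubtful benchmark, since it may be the expected TcB-SBR difference rather than a difference between tones. At the protocol's SD, moderate imbalance raises the error rate only to 6-10%.
- **This could be left to a SAP.** Section 10.2 mentions one. But the synopsis says the detailed statistical analysis plan is in section 10, and section 10.2 names the stratifier, so a choice has been stated.
- **Over-adjustment.** The caution in section 10.2 concerns mediators such as the indication for testing. Nothing in the protocol suggests that device model depends on a baby's skin tone.
- **A mean model cannot replace Bland-Altman.** This stands. Agreement includes spread, and section 5.1 cites a study with more variance in darker tones. Pooled limits also describe agreement as practised.

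**Conclusion.** The point holds in conditional form. As written, the Objective 2 tone comparison accounts for SBR method only, and device model, body location and hospital have no inferential or stratifying role in it. If devices or sites differ in bias and tone mix differs between them, part of that bias may pass into the tone effect or mask it.

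Size and direction cannot be derived from the documents. The illustrative 2-12 µmol/L rests on assumed gaps of 10-30 µmol/L and share differences of 20-40 points. The artefact is zero if devices agree or the tone mix is the same on each. The stronger readings, that hospitals' machines are known to disagree or that the tone result will be spurious, are not supported.

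**What to change.** In section 10.2, keep the tone-specific Bland-Altman bias and limits of agreement as planned, and add:

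1. A linear mixed model of the paired TcB-SBR difference, with skin tone, TcB device model, body location and SBR type as fixed effects (rare levels pooled) and hospital as a random effect. Let residual variance differ by tone, so that spread is not forced to be equal.
2. A statement that the between-tone comparison of bias rests on this model.
3. Bland-Altman results shown by device model.

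No new data are needed: device, location and SBR type are in Table 1, and the study identifier carries a site code. The cost is wording, code and some precision. The loss falls mainly on tone 4, assumed at 10% of babies, and arises where device is nested in hospital, because device and hospital effects are then hard to separate. Pairs may also be well below 560, since section 7 describes SBR following TcB only within a certain threshold of the treatment line.

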### 5.2. Rationale

The recent NHS Race and Health Observatory review of neonatal assessment and practice in Black, Asian and minority ethnic newborns highlights the potential for bias in the assessment of jaundice in neonates with darker skin tones. While multiple factors are likely to contribute to this, the failure to effectively detect jaundice in darker skinned neonates may play a role. In clinical practice, visual assessment remains a common indication for further jaundice investigations (e.g. TcB or SBR). The relationship between neonatal skin tone and jaundice assessment and diagnosis needs to be further explored.

Our first primary objective is to assess the level of first bilirubin measurement in neonates of different skin tones. This will enable us to determine if neonates with darker skin tones are only being assessed for jaundice once they have reached a higher bilirubin level, compared to lighter skinned neonates.

The second primary objective is to evaluate the agreement between TcB and SBR measurements in neonates of different skin tones.

During protocol development, parents and carers of infants in a range of London boroughs were invited to complete a survey to explore the need for the study including an exploration of parental experiences and concerns related to jaundice assessment in the context of different ethnic and racial backgrounds. Survey results represented a wide range of self-identified ethnic backgrounds and a significant proportion felt that their baby's ethnicity impacted their jaundice assessment, with a variety of reason why this might have been. We have used the results to inform protocol development in a number of ways. For example, to formulate focus group and semi-structured interview themes. Parent representatives also agree that the rationale for our study is well founded and the answers to the questions we have posed, will be valuable in the improvement of care for babies and families of all backgrounds.

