#### **Primary Objective 1**

We will be using a linear mixed effects model, where the confounders will be adjusted for as fixed effects, and hospitals will be fitted as a random effect. Due to the complexity of the model we will be using, the optimal method of calculating the sample size requirement *a priori* is with simulation, using *simr* in R^12. We use the following simulated dataset:

[figure not shown]
- Exposure Our exposure, skin tone, will be on 4 levels, with 1 being the lightest and 4 the darkest. No recent research on skin tone within London has been found, therefore we refer to the latest UK census results for ethnicity. For a conservative estimate, we will simulate the data for ethnicity that we would expect in London to act as a proxy for skin tone, as with the 6 categories of ethnicity (White (53.8%), Black (13.5%), Asian (20.7%), Mixed (5.7%) and Other (6.3%)). Therefore we simulate data with probability 50%, 20%, 20% and 10% for tones 1,2,3 and 4, respectively.
- We assume that we will have 20 hospitals collecting data, therefore we have 20 clusters to be a random effect
- The outcome will be simulated depending on skin tone and age. Age will be uniformly distributed between ages 0 and 96 hours. Bilirubin mean will be simulated according to the following formula:
  - Bilirubin (μmol/L)=2.6\*age (hours)+60+20\*skin tone+60 with standard deviation 10. The coefficient and intercept, 2.6 and 60 respectively, is to fit the line where babies begin to need phototherapy according to the NICE jaundice treatment threshold graphs.

We wish to achieve an effect size of 10 µmol/L for skintone 2 compared to skin tone 1, 20 µmol/L for skin tone 3 compared to skin tone 1, and 30 µmol/L for skintone 4

compared to 1. We perform 100 simulations for each simulated cluster size (between cluster sizes of 10 and 50 neonates), and estimate the average power achieved. Assuming a 95% confidence interval (CI), we can plot the number in each cluster against the estimated power.

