## **Primary Objective 2**

We approximate a sample size needed for Bland-Altman plots. We calculate the minimum sample size needed to detect a difference. A prior study found the following measurements:

	Mean [SD] (mcmol/L)
Colour 1	106 [43]
Colour 2	108 [38]
Colour 3	113 [38]
Colour 4	145 [34]

From this, we take a mean difference of 10 to be our estimated effect size. From above, we take the two largest standard deviations for a cautious estimate of the standard dedication of difference (SD= $\sqrt{43^2+38^2}=57.4$ ). We set our targeted clinical agreement limit at 145 mcmol/L. Under these assumptions, a sample size of 80% requires 140 study participants , which from above we should easily exceed.

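### Objective 2 compares TcB–SBR differences between skin tones with no term for bilirubin level, so any level-dependent TcB error would be mixed with a tone effect

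*Protocol*

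**What the plan says.** Protocol Section 10.2 gives the Objective 2 analysis: "Primary objective 2 will use the Bland-Altman to detect differences of measurement between skin tones". The only stratifier it names is the way SBR was measured. The outputs are the mean difference ("The mean of the differences will be provided with 95% CI"), the IQR of the difference with a p-value, rates of over- and under-estimation by tone, Bland-Altman plots, and sensitivity, specificity and ROC analyses. Age "shall be included as a fixed covariate in all models other than Bland-Altman". Bilirubin level is not named as a covariate or stratifier for Objective 2.

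Elsewhere the protocol treats level as something that may differ by tone:

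- Section 5.2 says Objective 1 will "determine if neonates with darker skin tones are only being assessed for jaundice once they have reached a higher bilirubin level".
- Section 10.1, Primary Objective 1: "The outcome will be simulated depending on skin tone and age". The targets are stated as "We wish to achieve an effect size of 10" µmol/L for tone 2, then 20 for tone 3 and 30 for tone 4, each against tone 1.
- Section 10.1, Primary Objective 2: "A prior study found the following measurements", followed by means of 106 for colour 1 and 145 for colour 4.

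**The concern.** Comparing mean TcB–SBR differences between groups isolates the effect of group only if the difference does not depend on bilirubin level, or if the groups have the same level. The protocol makes unequal levels its first primary question. If the Objective 1 hypothesis is true, the tone groups may well enter Objective 2 at different levels. Any tendency of TcB to read progressively low or high as bilirubin rises would then appear as a difference between tones, even if the device treated every skin tone alike. A real tone effect in the opposite direction could be cancelled.

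At stake is a co-primary conclusion about whether TcB reads differently in darker skin.

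**Working it through.** **The plan's own figures.** The point rests on no figure in the sample-size calculation. For completeness, √(43² + 38²) = 57.4 reproduces. The 140 participants do not: the Bland-Altman sample-size method, with an assumed two-sided alpha of 0.05, gives 152. That is a separate matter.

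**Size of the artefact.** Let b be the slope of (TcB − SBR) on bilirubin level and G the gap in mean level between two tones. With no true tone effect, the expected raw contrast is b × G.

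- G = 30: the tone 4 versus tone 1 target in Section 10.1.
- G = 145 − 106 = 39: colour 4 versus colour 1 in the prior-study table.
- b: not in the documents, so assumed at 0 to 0.3. The artefact takes the sign of b.

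| Assumed b | G = 30 | G = 39 |
|---|---|---|
| 0 | 0 | 0 |
| 0.1 | 3 | 3.9 |
| 0.2 | 6 | 7.8 |
| 0.3 | 9 | 11.7 |

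Units are µmol/L.

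**Effect on a test.** Tone 4 versus tone 1 was simulated with no true tone effect, G = 30, negative slopes, the protocol's 50% and 10% shares, and an assumed level SD of 40. False-positive rates of the raw comparison for b of size 0, 0.1, 0.2 and 0.3:

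- all 560 paired, assumed SD of differences 25: 0.06, 0.12, 0.33, 0.58;
- all 560 paired, SD 57.4: 0.06, 0.07, 0.12, 0.20;
- 140 pairs, SD 25: 0.04, 0.08, 0.13, 0.19.

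Adjusting for level brought the contrast to within 1 µmol/L of zero and the rate to 0.04–0.06. However, that simulation adjusted for a level known without error, which no real analysis has.

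**Does adjusting for the TcB/SBR mean solve it?** Not by itself. Take no bias at any level in either tone (b = 0, no tone effect), so the raw contrast is 0. Assume a true-level SD of 38, SBR error SD of 5, TcB error SD of 20 and G = 39.

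- Slope of the difference on the mean = [(20² − 5²)/2] / [38² + (20² + 5²)/4] = 187.5/1550.25 = 0.121.
- Adjusted contrast = −0.121 × 39 = −4.7 µmol/L, which is entirely spurious.

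Now let the tone 4 TcB error SD be 30, with separate slopes by tone:

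- Tone 4 slope = 437.5/1675.25 = 0.261.
- Contrast at the midpoint level of 125.5 = 0.261 × (−19.5) − 0.121 × 19.5 = −7.5 µmol/L.

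Using SBR as the level term in the first of these cases, the slope is −5²/(38² + 5²) = −25/1469 = −0.017, and the contrast is only +0.7. But SBR fails where the mean works. With an assumed error SD of 20 in both methods, the mean has slope 0, while SBR has slope −400/1844 = −0.217 and gives a contrast of +8.5. Neither level term is safe in all cases.

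**The case against.** The strongest reply is that the decisive premise is not in the documents. No section reports that TcB–SBR differences change with level. The background in Section 5.1 reports greater variance in darker tones and overestimation in non-caucasian babies, and neither is a level effect. At zero slope there is no artefact. This stands, and it makes the harm conditional.

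The gaps are also uncertain. The 10/20/30 values are detection targets, not predictions. The prior-study table does not say whether its means are TcB or SBR. Objective 2 can use only babies with both measurements. Section 7 says SBR follows a TcB near the treatment line, so the gap among paired babies may differ from the gap among all first measurements. All of this stands.

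Next, Bland-Altman plots show difference against mean, so a trend could be seen, and Section 10.2 excludes age rather than level. The analysis plan may add a level term. Both are fair, but the between-tone statistics that the protocol names would not separate level from tone, and the synopsis points to Section 10 for the detailed analysis plan.

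Finally, regressing on the TcB/SBR mean can create a false tone effect where the raw comparison has none. The working confirms this, and it changes the remedy.

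A reader might infer that Objective 2 cannot answer its question, or that the artefact amounts to the planned effect of 10 µmol/L. The documents support neither. Agreement within each tone at the levels encountered remains a valid result, as do the other Section 10.2 outputs. The 10 µmol/L enters a Bland-Altman sample size, where a mean difference is ordinarily between methods, so it is not clearly comparable with a between-tone contrast.

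**Conclusion.** The point holds in conditional form. The protocol fixes a between-tone comparison of mean TcB–SBR differences without bilirubin level, while asking in its other primary objective whether level differs by tone. If the difference depends on level, the raw contrast is confounded by 3 to 9 µmol/L for a 30 µmol/L gap, or 3.9 to 11.7 for a 39 µmol/L gap, at assumed slopes of 10% to 30%. It is not confounded at a slope of zero, or if paired babies have equal levels across tones. The false-positive rates further depend on the assumed SDs and the number of pairs. The documents do not show that confounding will occur; they show that the planned contrast could not tell it from a tone effect. The remedy is cheap, so it should be made.

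**What to change.** Keep the raw Bland-Altman results by tone as planned. Beside them, pre-specify a level-aware comparison: regress TcB − SBR on tone, bilirubin level, tone-by-level and serum method, with hospital as a random effect. Report bias and limits of agreement by tone at common bilirubin levels.

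Do not rely on the TcB/SBR mean alone as the level term. Fit the model once with the mean and once with SBR, or use an errors-in-variables method. Call a difference a tone effect only if it is consistent across them. Put this in Section 10.2 and keep the analysis plan in line.

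Cost: analysis wording and a little analysis work, using data already listed in Table 1. The downsides are a few more parameters, results that depend on the choice of level term, and imprecise interaction terms in tone 4. At the assumed 10% share, tone 4 would supply about 56 of 560 pairs, or 14 of 140.

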# 7. Study population

The annual number of deliveries per NHS Trust in England ranged from 3,000 to 13,000 in the year 2022 to 20239. NICE guidance recommends that all newborn babies are examined for jaundice at every opportunity, especially in the first 72 hours5. If jaundice is suspected, a bilirubin level should be measured. This is primarily done by midwives either in the community or in a secondary care setting. While exact guidelines vary within secondary care settings, TcB is commonly used in neonates over 24 hours of age who visibly appear jaundiced or meet a risk factor for jaundice1. TcB measurements within a certain threshold of the phototherapy treatment line should then undergo SBR testing5. As jaundice affects approximately

60% of term newborn babies, sufficient numbers of patients are expected to meet study inclusion criteria during a short timeframe.

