## **Screening and recruitment:**

- On data collection days, staff members carrying out jaundice assessments in relevant inpatient areas will be notified and asked to alert the research team when any neonates are undergoing their first TCB or SBR
- Standard clinical care will not be delayed for enrollment
- Identification of potential eligible babies will occur via a written identification table in postnatal areas. Outcomes, i.e. included or excluded, and reasons for exclusion will be noted in the infant's clinical record.
- The research team at each site will consist of the local lead and a number of additional data collectors who have undergone training. These individuals will review whether or not these neonates meet the eligibility criteria, and approach the birthing parent to discuss the study if eligible
- Study data will be collected in participants where all eligibility criteria are met

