#### **Laboratory assessments:**

No additional laboratory assessments will be carried out on participating neonates by the research team. SBR measurements will only be done by the normal clinical team as part of routine clinical care.

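### TcB-SBR pairs arise mainly in infants whose TcB prompted an SBR, so uncorrected Bland-Altman bias, specificity and ROC results are distorted, possibly by different amounts in different skin tones

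*Protocol*

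**What the plan says.** Protocol Section 10.2 sets the method: "Primary objective 2 will use the Bland-Altman to detect differences of measurement between skin tones", stratified by how SBR was measured. It asks for mean differences with 95% CIs and for over/under-estimation rates by tone, and continues: "Bland-Altman plots will be reported as well as Specificity and sensitivity analyses using Receiver operating characteristic (ROC) curves".

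Three other places decide which infants supply a pair:

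- Section 9, Laboratory assessments: "No additional laboratory assessments will be carried out on participating neonates by the research team", and "SBR measurements will only be done by the normal clinical team as part of routine clinical care".
- Section 7 on routine practice: "TcB measurements within a certain threshold of the phototherapy treatment line should then undergo SBR testing". It also says that practice differs between sites: "While exact guidelines vary within secondary care settings, TcB is commonly used in neonates over 24 hours of age".
- Section 9, Screening and recruitment: staff are "asked to alert the research team when any neonates are undergoing their first TCB or SBR". One measurement is enough to enter; a pair is not required.

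On missing data, Section 10.2 says "We expect limited missing data". It allows complete-case analysis below 5% missing and multiple imputation above 5%, framed by covariate or category. An SBR that was never clinically indicated is not mentioned. Section 10.2 does discuss collider bias, but only for covariate adjustment.

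**The concern.** The reference measurement is obtained largely because of the value of the index measurement. Keeping pairs with a high TcB keeps more of the infants whose TcB error happened to be positive, so the mean of TcB minus SBR is pushed upwards even for a device with no bias. Many true negatives with a low TcB never get an SBR and drop out of the specificity denominator. Infants with a low TcB and a high SBR are seldom verified.

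The distortion need not be equal across tones. It depends on how far below the line the first test falls, on the TcB error variance and on the local SBR threshold. The protocol gives reason to expect differences in each:

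- Section 10.1 assumes first bilirubin 10, 20 and 30 µmol/L higher in tones 2, 3 and 4 than in tone 1.
- Section 5.1 cites a study with greater variance in darker tones.
- Section 8 extracts SBR thresholds from local guidelines in order to describe how they vary.

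A primary objective could therefore report a skin-tone difference in device bias, or hide one, through referral patterns alone.

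**Working it through.** **The plan's own figures.** The protocol gives no verification share, trigger distance or TcB error SD, so it has no figure for this bias to reproduce. Its one Objective 2 figure is 140 participants. The stated inputs (difference 10, SD 57.4, limit 145, 80% power, two-sided 5% assumed) give 152; an SD rounded to 57 gives 141. That is a separate, minor matter. For scale, 140/560 = 25%, so reaching 140 needs a quarter of infants to have both tests.

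**Mean difference under selection.** All inputs in this step are assumptions. Let SBR be S ~ N(m, 40²) and TcB be T = S + error, with error ~ N(0, e²), so true bias is 0. A pair is kept if T ≥ c. With a = (c − m)/√(40² + e²),

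E[T − S | T ≥ c] = e²/√(40² + e²) × λ, where λ = φ(a)/(1 − Φ(a)).

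λ is 1.159, 0.644 and 0.195 when the top 30%, 60% and 90% of TcB values get an SBR.

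| e | e²/√(1600 + e²) | 30% | 60% | 90% |
|---|---|---|---|---|
| 20 | 400/44.72 = 8.94 | +10.4 | +5.8 | +1.7 |
| 25 | 625/47.17 = 13.25 | +15.4 | +8.5 | +2.6 |
| 30 | 900/50 = 18.0 | +20.9 | +11.6 | +3.5 |

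Apparent over-reading runs from about 2 to 21 µmol/L and shrinks as the trigger widens.

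**Different tones, identical zero bias.** Assume the first test averages 80 below the line and SBR follows if TcB is no more than 50 below it.

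- e = 25: a = (80 − 50)/47.17 = 0.636, λ = 1.242, 26% have a pair, bias 13.25 × 1.242 = +16.5.
- First test 30 µmol/L higher (the Section 10.1 shift for tone 4): a = 0, λ = 0.798, bias +10.6.
- Original mean, e = 35: a = 30/53.15 = 0.564, λ = 1.189, bias 1225/53.15 × 1.189 = +27.4.

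The spurious gaps are 16.5 − 10.6 = 5.9 and 27.4 − 16.5 = 10.9. They act in opposite directions: later detection shrinks the artefact and wider error enlarges it. The net direction by tone is therefore unknown.

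**Accuracy measures** (simulated). With S ~ N(150, 40²), e = 25, case S ≥ 190 and positive T ≥ 190, specificity is 0.91 in all infants. In pairs it is 0.65, 0.81, 0.87 and 0.89 for triggers 25, 50, 75 and 100 below the cut-off. In the 80-below-the-line scenario with e = 25, AUC is 0.89 in pairs against 0.97. Sensitivity moves little there (0.706 against 0.701); with the trigger 25 below the cut-off it rises from 0.75 to 0.80.

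**Would regression of SBR on TcB avoid the problem?**

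- *Age is needed.* The trigger is relative to a line that Section 10.1 models as rising 2.6 per hour. Assume age uniform over 24 to 96 hours and e = 25. Variance due to age is 2.6² × 72²/12 = 2920. The slope without age is (2920 + 1600)/(2920 + 1600 + 625) = 0.88 in all infants. It becomes 0.93 to 0.96 in selected infants when mean SBR lies 40 to 80 below the line and the trigger is 50 below. With age in the model it is 1600/2225 = 0.72 in both.
- *The tone coefficient is not device bias.* With the same unbiased device in every tone and the 30 µmol/L shift, the tone 4 coefficient is 30 × e²/(1600 + e²). That is 6.0, 8.4 and 10.8 for e = 20, 25 and 30, with or without selection on TcB.

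**The case against.** **Not every pair follows a TcB near the line.** A reader might infer that pairs exist only there. The documents do not support that: Section 7 describes what should happen, says guidelines vary, and SBR may be taken for other clinical reasons. This softens the bias without removing it. With e = 25, the top 30% verified and a random 20% of the rest also verified, the mean error among the rest is −0.3 × 15.4/0.7 = −6.6. The paired bias is (0.3 × 15.4 − 0.14 × 6.6)/0.44 = +8.4.

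**The sizes are assumed.** This stands. The lowest specificity above comes from one narrow trigger. A contrast such as 30% referral in one tone and 60% in another has no documentary basis. The difference of 10 in Section 10.1 feeds a Bland-Altman sample size and is not stated as a between-tone difference in bias, so it is no yardstick for the spurious gaps.

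**Regression should replace Bland-Altman.** This is tempting because selection on TcB and age leaves the relation of SBR to TcB intact. But the synopsis and Section 5.2 state the objective as agreement (Section 6.1 says relationship), and the tone coefficient mixes device behaviour with the bilirubin differences that Objective 1 looks for. In the shift scenario with SBR if TcB ≥ 165 and a tone 1 mean of 150, the selected Bland-Altman gap between tones 1 and 4 is about 4 to 7, smaller than the regression's 6 to 11.

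**Objective 2 is meant to set the TcB level that calls for SBR.** Section 5.1 reports this as an outside review's research recommendation; the objective does not say it.

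**A separate SAP, or the imputation rule, may deal with it.** The synopsis places the detailed plan in Section 10, and Section 10.2 already fixes these statistics. Imputing SBR from TcB could help in principle, but the rule as written does not treat a non-indicated SBR as missing.

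**Conclusion.** The point holds in direction. SBR comes only from routine care, mainly after a TcB near the line, and Section 10.2 compares paired statistics between tones without correction. Under this selection an unbiased device appears to over-read, and specificity and AUC are understated. Sensitivity at a cut-off above the trigger changes little; below the trigger, pairs say little about it.

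The size cannot be settled from the protocol. About 2 to 21 µmol/L rests on normal errors, SBR SD 40, TcB error SD 20 to 30 and SBR in 30% to 90% of infants; larger error or narrower triggers go beyond it. Differences between tones are possible in either direction and are not shown to occur. It would be wrong to conclude that any observed tone difference must be an artefact, or that Bland-Altman should be abandoned.

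**What to change.** Amend the Primary Objective 2 text in Section 10.2:

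1. Keep Bland-Altman by tone, state that it applies to infants sent for SBR, and report the share with a paired SBR by tone and site.
2. Do not present uncorrected sensitivity, specificity or ROC results as device accuracy. Where some infants below the trigger were verified, give verification-corrected values (Begg-Greenes, or inverse-probability weighting on TcB, age, gestation, site and tone). Otherwise omit them.
3. Add, as a supporting prediction analysis and not in place of agreement, a regression of SBR on TcB with tone, tone × TcB, age, gestation, SBR method and hospital. State that its tone coefficients also reflect differences in underlying bilirubin and do not measure device bias.

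The cost is more analysis work and weaker claims for infants below the SBR trigger. Table 1 already collects the patient-level variables, and no extra blood test is needed. Local SBR thresholds are available only where sites submitted guidelines, so the weighting should use site rather than depend on a known threshold.
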